3.11. CONFIDENTIAL INTERIM ANALYSIS FOR DECISION MAKING FOR PHASE II DESIGN

An interim analysis will be performed when culture results are available from twenty-eight days after vaccination of the high dose group 3. The interim analysis will provide summary data only (i.e. no information about individual volunteers) for the sponsor/ILiAD to present to regulatory agencies, partners, and funding sources to aide in designing and planning a Phase II study.

Descriptive statistics will be provided for demographic and other baseline characteristics.

COLONIZATION

The frequency of colonization of the human respiratory tract by live attenuated B. pertussis strain (BPZE1) and its magnitude (in terms of colony forming units, CFUs) will be summarized for each group. Descriptive statistics for the CFUs, including the mean, standard deviation, minimum, maximum, median, and 95% confidence intervals will be constructed and reported.

SYMPTOMS FROM THE RESPIRATORY TRACT

Cough, spasmodic cough and any symptom from the respiratory tract will be summarized using counts and percents for each of the vaccine groups and between the groups of colonized and non-colonized individuals.

HEMATOLOGY

Pre- and post-vaccination values of cell blood counts (haemoglobin, total and differential WBC, RBC and platelets) will be summarized for each group separately. Descriptive statistics, n, mean, standard deviation, minimum, maximum, median, and 95% confidence intervals will be constructed and reported.

REFERENCES

1. Guideline ICH - E9: Statistical Principles for Clinical Trials. 1998.
2. Guideline ICH - E3: Statistical Principles for Clinical Trials. 1995.
5. Basic Statistical Reporting for Articles Published in Biomedical Journals: The « Statistical Analyses and Methods in the Published Literature » or The SAMPL Guidelines” | The EQUATOR Network [Internet]. [cité 9 mai 2014]. Disponible sur: <http://www.equator-network.org/reporting-guidelines/sampl/>

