If no primary safety endpoint event is observed among 36 volunteers (pooled across groups 1,2,3), then the upper bound of the 95% confidence interval for the event rate would be 10%.

XV.2. STATISTICAL METHODS

XV.2.1. Analysis strategy

Statistical analyses will be performed by the EUCLID Clinical Trials Platform (except for the interim analysis of the colonization and safety data when culture results are available from twenty-eight days after vaccination of the high dose group 3, mentioned below).

All participants having received at least one injection will be included in the analysis. All primary analyses will be performed per dose group and randomized allocation (for arms receiving active vaccination) and for the pooled placebo arms (unless there is evidence for a time trend in placebo observations between group).

The main analysis of the primary endpoint is conducted:

- By modified intention to treat: This means that all randomized participants who received a vaccine dose are included in the analysis in the group and intervention arm to which they were initially randomized and all their data is used regardless of protocol deviations during the trial/study.
- In this analysis, participants with missing follow-up data will be assumed to be event-free, unless the site has any knowledge of a safety event having occurred and has notified this in the e-CRF.

No statistical comparisons between dose groups or randomized allocations will be performed but two-sided 95% confidence intervals will be displayed..

Intra-group statistical comparisons will be performed for immunogenicity markers.

In ancillary analyses, appropriate statistical models for the analysis of longitudinal data may be used to estimate the slopes of changes in immunogenicity markers per group. Methods for high-dimensional data may be used to assess the interrelationships between different immunogenicity markers.

Quantitative variables

Quantitative variables will be described in terms of absolute frequency, median, interquartile range, minimum, and maximum.

Intra-group comparisons will be made using paired Student t-test or Wilcoxon paired signed-ranks test according to the distribution of variable of interest for analyzing change from baseline to post-vaccination within a given dose group or randomized allocation. Transformations to normalize the variables can be made if necessary.

Qualitative variables

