Qualitative variables will be described in terms of number, proportion and exact binomial confidence interval of proportion.

Intra-group comparisons will be made using McNemar test or other, depending on the number of modalities of the variables of interest.

Titers

Geometric means and their 95% confidence interval will be calculated for titers.

XV.2.2 Analysis software

Analyses will be performed using SAS® software (version 9.3 or higher) and R software.

XV.2.3 Analysis plan

A detailed statistical analysis plan will be established before the first statistical analyses of the trial.

Descriptive statistics will be provided for demographic and other baseline characteristics.

Hematology

Pre- and post-vaccination values of cell blood counts (haemoglobin, total and differential WBC, RBC and platelets) will be described for each group separately. Within group comparisons may be done using appropriate tests for paired measurements.

Primary Safety endpoint

The primary endpoint will be described per group and randomized allocation, in modified ITT population, with participants with missing follow-up data considered event-free in primary analysis. Numbers, percentages and 95% confidence intervals will be shown. Each individual component of the primary endpoint will also be described.

Secondary endpoints

Secondary endpoints will be described per group and randomized allocation, displaying numbers, percentages and 95% confidence intervals (qualitative variables); medians and interquartile intervals (quantitative variables) or geometric mean and 95% confidence interval (antibody titers).

Number, time of occurrence and duration of secondary safety endpoints will be described.

Colonization endpoints will be described (number and proportion of participants with colonization at each post-vaccination visit; number of visits during which bacteria are detected; magnitude of bacterial colonization (number of cfu) per post-vaccination visit)

Pre- and post- vaccination serum IgG and IgA antibody endpoints will be described per group and randomized allocation. Within group comparisons may be done using appropriate tests for paired measurements.

Cough, spasmodic cough and any symptom from the respiratory tract, as well as antibody titers, will be described for each of the vaccine groups and the pooled placebo group, and for the groups of colonized and non-colonized individuals.

Exploratory endpoints

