2.1.3. OTHER SECONDARY ENDPOINT

1) Colonization of the BPZE1 strain in the nasopharyngeal mucosa:

Per dose, group and randomized allocation:

- Number and proportion of participants who have been colonized by the modified *B. pertussis* strain BPZE1 at each post-vaccination visit
- Number of visits during which bacteria are detected
- Magnitude of bacterial colonization (number of cfu) per post-vaccination visit
- Cough, spasmodic cough and any symptom from the respiratory tract will be described for colonized and not colonized participants

2) Immunogenicity:

Per dose, group, colonized/not colonized and randomized allocation:

- IgG and IgA antibodies against PT, FHA, PRN, and fimbriae 2/3 in serum at visits 2, 4, 6, 7, 8, 9 and 10
 - Geometric mean levels
 - Number and proportion of participants with positive responses, defined by at least 100% increase from pre- to post-vaccination, to at least 4 times MLD after vaccination

Samples will be tested blindly for *pertussis* specific antibodies in batch for each group. Antibody levels to PT, FHA, PRN, and fimbriae 2/3 will be expressed in IU/mL calibrated against reference antisera from the National Institute for Biological Standards and Controls.

- **Analysis strategy**

The immunogenicity criteria analysis will be performed on the mITT population and based on available data (without missing data handling) with the hypothesis of MCAR.

A robustness analysis will be performed and missing values will be imputed by the median of immunogenicity values in the placebo group.

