2.2. STATISTICAL METHODS

2.2.1. DESCRIPTIVE ANALYSIS

The frequency and proportion of available data are described for each variable.

Quantitative variables will be described in terms of absolute frequency, mean, standard deviation, confidence interval of the mean, median, interquartile range, minimum, and maximum. Geometric means and their confidence interval will be performed for titers.

Qualitative variables will be described in terms of number, proportion and exact binomial confidence interval of proportion.

Descriptive analysis is performed overall and by intervention group.

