2.2.2. COMPARATIVE ANALYSIS

No statistical comparisons between arms or cohorts will be performed, as the trial is not designed for such comparisons. Intra-group comparisons will be performed for immunogenicity endpoints.

Intra-group comparisons for quantitative variables will be made using paired Student t-test or Wilcoxon paired signed-ranks test according to the distribution of variable of interest for analyzing change from baseline to post-vaccination within a given cohort arm. Transformations to normalize the variables can be made if necessary.

Intra-group comparisons for qualitative variables will be made using McNemar test or other, depending on the number of modalities of the variables of interest.

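### The interim plan points to a confidence interval for the untransformed mean colony count, which can cover well below 95% with 12 per dose; a log-scale summary would be safer

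*Combined protocol and SAP*

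**What the plan says.** CFU magnitude is a secondary endpoint, listed in SAP 2.1.3 as "Magnitude of bacterial colonization (number of cfu) per post-vaccination visit".

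Three places govern how it is summarized:

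- **SAP 3.11** (confidential interim analysis, Colonization), for each group: "Descriptive statistics for the CFUs, including the mean, standard deviation, minimum, maximum, median, and 95% confidence intervals will be constructed and reported". The IQR is not listed.
- **SAP 2.2.1**, for quantitative variables in general: "Quantitative variables will be described in terms of absolute frequency, mean, standard deviation, confidence interval of the mean, median, interquartile range, minimum, and maximum". It then adds: "Geometric means and their confidence interval will be performed for titers".
- **Protocol XV.2.1**: "Quantitative variables will be described in terms of absolute frequency, median, interquartile range, minimum, and maximum". Protocol XV.2.3 likewise describes quantitative secondary endpoints by a median and interquartile interval, with geometric means for antibody titers only.

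SAP 2.2.2 does say "Transformations to normalize the variables can be made if necessary", but under intra-group comparisons, not under descriptive summaries. No section says how a culture-negative result enters the CFU summary. SAP 3.11 also does not say whether the four placebo recipients in groups 1–3 are part of the group figure.

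**The concern.** Bacterial counts contain zeros and may be strongly right-skewed. In a group of 12, one heavily colonized participant can then set both the arithmetic mean and its standard error. A symmetric interval around such a mean tends to miss on one side, lying wholly below the true mean, and it can extend below zero, which is impossible for a count.

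The SAP uses a geometric mean for titers and medians for cytokines and spot-forming units, so CFU is left with the least suitable summary. Under SAP 2.1.6 and 3.11 the output goes to regulators, partners and others planning Phase II as summary data only. Those readers cannot recompute a better interval from individual values. What is at stake is how precisely, and how high, colonization at each dose appears to them.

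**Working it through.** **Inputs from the documents.** Each of groups 1–3 has 12 active and 4 placebo recipients (SAP 1.2.1). In the earlier trial 5 of 12 were culture-positive at 10^7 cfu, which is the lowest dose here (protocol III.2). Protocol III.2 also names colonization above 70% as the level of interest. The documents give no mean, SD or distribution for CFU and no coverage figure, so there is no plan figure to reproduce on this point.

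**Assumptions.** The interval is the two-sided 95% t-interval for the arithmetic mean. Counts among culture-positives are log-normal and culture-negatives are zero. The log10 SD among positives is unknown and is ranged from 0.1 to 1.5. The probability of being positive is set at 100%, 70% or 42% (5/12).

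**Step 1: coverage by simulation.** The interval is x̄ ± t(0.975, n−1)·s/√n. The true mean is p·exp(σ²/2), with σ = log10 SD × ln 10. With n = 12 and 100,000 simulated groups per cell, coverage (%) is:

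| log10 SD | 0.1 | 0.25 | 0.5 | 0.75 | 1.0 | 1.5 |
|---|---|---|---|---|---|---|
| 100% positive | 94.5 | 91.6 | 81.5 | 66.6 | 49.4 | 20.3 |
| 70% positive | 94.2 | 93.2 | 80.7 | 63.4 | 46.1 | 18.1 |
| 42% positive | 93.9 | 90.4 | 76.7 | 58.7 | 40.8 | 15.3 |

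From SD 0.5 upward almost all misses put the whole interval below the true mean. At SD 0.5 and 70% positive, for example, 19.2 of the 19.3 percentage points of error are on that side. The lower limit is negative in 13–74% of groups at SD 0.5 and in 71–96% at SD 1.0.

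Including four placebo zeros (n = 16) changes little: 82.4, 80.3 and 75.7% at SD 0.5, and 48.9, 45.8 and 40.4% at SD 1.0.

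**Step 2: a result that needs no assumed spread.** Suppose k of 12 are positive. For a given total, the standard error is smallest when all positive counts equal one value c. The lower limit is then (c/12)·[k − 2.201·√(k(12−k)/11)].

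- k = 3: 3 − 2.201·√(27/11) = 3 − 3.45, negative.
- k = 4: 4 − 2.201·√(32/11) = 4 − 3.75, positive.

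Unequal counts only lower the limit. So with one, two or three positives among 12 the lower limit is below zero for any distribution, and with none the interval collapses to zero. With 16 per group the result at k = 3 is the same: 3 − 2.131·√(39/15) = 3 − 3.44.

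This case is realistic at the lowest dose. The 5/12 in the earlier trial counts anyone ever positive, and the share positive at a single visit cannot exceed that. At a per-visit probability of 5/12, the binomial chance of one to three positives among 12 is 0.013 + 0.052 + 0.124 = 0.19.

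**Step 3: the alternative.** A t-interval on log10 CFU among positives, back-transformed, covers 94.9–95.1% at n = 5, 8 and 12 (log10 SD 1.0, same log-normal assumption). With very few positives it becomes uninformative. The log10 half-width is t·SD/√k, which is 2.5 SD at k = 3 (4.303/√3) and 9.0 SD at k = 2 (12.706/√2).

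**The case against.** The strongest reply is that SAP 3.11 does not prescribe a faulty interval. It gives no scale and does not say what the interval is for, so both the untransformed scale and the t-method are inferences. This stands as a limit on certainty. Even so, SAP 2.2.1 ties the interval to the mean and reserves geometric means for titers, so the untransformed mean is the natural reading.

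Second, the size rests on a spread the documents do not give. That also stands. A reader might infer that coverage is bound to be far below 95%, but at a log10 SD of 0.1–0.25 it is 90–95%. Likewise, the interval cannot be said usually to include negative counts, since that too varies with spread and with the number positive.

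Third, much of a sound summary is already planned. The median, minimum and maximum appear in SAP 3.11, the proportion colonized at each visit in 2.1.3 and 3.8, and exact intervals for proportions in 2.2.1. A single extreme value would therefore show. This reduces the harm but does not correct an interval printed beside the median.

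Fourth, a geometric mean among positives answers a different question and fails when few are positive. That is correct, and the fix has to provide for it.

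**Conclusion.** The point holds as a reporting weakness that should be corrected. The SAP points to an interval for the untransformed mean CFU, contrary to the protocol's median and interquartile interval. Its coverage with 12 vaccinees runs from near nominal to 15–20% over an assumed log10 SD of 0.1 to 1.5. The negative lower limit with one to three positives needs only the t-interval assumption. The coverage figures also need the log-normal assumption and the assumed spread.

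A reader might go further and infer that dose escalation, the primary safety result or the choice of Phase II dose is compromised. The documents do not support that. SAP 2.2.2 rules out comparisons between arms or cohorts, no decision rule uses the CFU mean, and the colonization level named in protocol III.2 is a proportion. Nor is CFU magnitude shown to be the main interim output, since SAP 2.1.6 and 3.11 also cover safety, symptoms and hematology. The interim report is confidential, not published.

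**What to change.** In SAP 3.11, and for CFU under 2.2.1, specify the following per visit and by dose and randomized allocation, with placebo separate from active:

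1. The proportion culture-positive with an exact 95% interval.
2. Among positives, the geometric mean CFU with a 95% interval computed on log10 values and back-transformed. Where there are too few positives for a useful interval (for example fewer than 3), give individual values or the range only. At the interim, give only what the no-individual-data rule allows.
3. The median, IQR and range over all participants, with culture-negatives counted as zero.

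If an arithmetic mean is kept as a measure of average burden, show it without the normal-theory interval.

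The cost is SAP wording and table shells, with no new data. The downside is that the geometric mean describes colonized participants only, so it must always be shown with the proportion positive.
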